**Retention.** The research assistant will track participant retention, which will be reviewed weekly by the principal investigator. We will collect extensive locator information at baseline (that contains contact information for at least two individuals with whom the participant is in regular contact) for participants in the event that they move or discontinue HIV care at the recruitment site, or become lost to follow-up from study procedures. Locator form information will be collected either in person or via Zoom. Should the individuals listed on the locator form be contacted, reference to HIV will never be made. We will make concerted efforts to maintain contact with individuals who discontinue the intervention but are still willing to complete follow-up assessments. To facilitate such retention, if necessary we will meet with participants at any confidential location that is comfortable for them for study assessment visits. Additionally, we have budgeted for financial incentives and public transportation costs.

**Fidelity:** All sessions led by the group facilitators will be audio-taped. Monitoring of the intervention will take into account both therapist adherence as well as competence. We have developed a rating checklist for therapist adherence including whether the specific components of the modules of treatment were delivered, as well as a contamination checklist to measure the degree to which group facilitators introduced intervention content into the control sessions. This will be done by the PI ([name]) or clinical supervisor. At least ten percent of the sessions will be reviewed.

**Assessment instruments:** All assessments that occur post treatment will be conducted by a study team member who did not serve as the group facilitator to minimize the risk of bias. We expect the baseline assessment, post-treatment assessment, and 3-month follow-up assessment to each last approximately 45-60 minutes.

**Sociodemographic data:** Data on age, race/ethnicity, relationship status, occupational status, and socioeconomic status will be collected at baseline, as will disclosure of HIV status and history of exposure to traumatic events, including interpersonal violence. Participant zip codes will also be recorded to account for time traveled to study visits.

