**Feasibility:** To assess feasibility, we will track the number of potential participants we screen, the number of potential participants who meet study inclusion criteria, the number of participants who meet study criteria and then enroll (and the time it takes to complete these steps), and the number of treatment and assessment sessions completed by all enrolled participants. We will also track the duration of assessments, reasons for declining enrollment and for prematurely leaving the trial, and make-up sessions attended. The study team will review these data and

determine the degree of feasibility, though we will consider these feasibility/retention outcomes in the context of what other trials conducted with older individuals living with HIV have achieved.

Acceptability: Acceptability will be assessed at post treatment using the eight-item Client Satisfaction Questionnaire (CSQ-8), a measure of how much an individual values a treatment. Items assess factors such as the perceived quality of the services, how much the services met needs, satisfaction with the help received, and others. Items are scored from 1 (poor) to 4 (excellent), with higher scores indicating greater satisfaction. We will also ask participants about their perceptions of the burden of the study assessment battery.

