#### Secondary Outcomes: HIV/Physical Health.

The proposed content on how to manage health in the context of HIV (See Table 3) provides information on the importance of sustained adherence to antiretroviral therapy and continued engagement in HIV care, as one must adequately manage their disease to be truly resilient in the face of HIV infection. Individuals will generate plans and back-up plans on how to manage common barriers to antiretroviral adherence, as well as engagement in HIV care. Thus, we will assess variables related to HIV management, to measure the performance of this content. Data

on time since HIV diagnosis will be assessed at baseline. The following variables will be assessed: current antiretroviral therapy regimen, adherence to antiretroviral therapy regimen, and engagement in HIV care.

*Engagement in HIV care:* On average, persons living with HIV should meet with their HIV provider four times per year. We will ask participants when they last saw an HIV care provider.

*Adherence to antiretroviral therapy:* Adherence will be assessed via self-report. Data on self-reported adherence will be collected each week using the participant “weekly adherence to skills” forms described below. The questions will be based on standardized questions for self-report assessment of adherence to antiretroviral therapy. A list of common antiretroviral medications will be provided along with the adherence assessment in order to facilitate participant memory and enhance self-report.

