*Cognitive status:* Cognitive status will be assessed using the Mini-Cog. The Mini-Cog can quickly detect cognitive impairment through its three-item recall test and a clock-drawing test (CDT) administered by a clinician. Respondents score as positive for cognitive impairment if they recall no words, or recall 1 or 2 words with an abnormal CDT. Both measures have been used with older adults in various health care settings, and previous research has found consistently good reliability and validity.

*Weekly adherence to skills:* Practice notes have been developed to correspond with each module of the 3RP treatment. Participants will be asked to keep brief daily diaries of their out of session practice (e.g., completion of 15 minutes of meditation, engaged in activities to foster social connectedness, engaged in a desired lifestyle behavior, etc.). These diaries will be used to generate a rating of adherence to out of session practice guidelines. If group sessions are conducted virtually via Zoom, participants in the intervention group will be mailed an envelope

containing weekly practice notes to be completed during the 10-week group program. Participants will then be asked to mail back the completed practice notes (via a pre-paid envelope) at the end of the program.

*Treatment Credibility and Expectancy:* The Treatment Credibility/Expectancy Questionnaire (CEQ) is a widely used 6-item measure that assesses treatment credibility and expectancy. Participants are asked to rate the treatment from 1 (not at all) to 9 (very much) and from 0% (not at all) to 100% (very much). The percentage ratings are subjected to linear transformation with a minimum of 1 and a maximum of 9. We will administer the scale after the first treatment session.

*COVID-19-related:* Quantitative assessments and the qualitative exit interview will contain COVID-19-related items in order to better understand the impact of COVID-19 and corresponding public health restrictions on participants' lives (e.g., mental health, ability to adhere to HIV medications), and their experience participating in this study.

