### **Data monitoring.**

Data collection occurs in the form of a series of quantitative assessments and qualitative interviews. The principal investigator ([name]) will work closely to oversee all data management and analysis issues, along with the project statistical ([name]) and the rest of the study team. The study staff will review all data collection forms on an ongoing basis for data completeness and accuracy as well as protocol compliance. Data verification will be performed weekly by a study research assistant who will not be involved in data collection or have any direct contact with study participants. All intervention sessions and exit interviews will be audiotaped (participant consent will be obtained). Intervention fidelity will be assessed by randomly selecting approximately 10% of sessions and assessing adherence to the protocol based on checklists and scales specifically developed for this study. The group facilitator will also participate in weekly supervision with [name], [name] or a study staff psychologist, where audio of sessions will also be reviewed.

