For depressive symptoms, Ickovics et al. reported that 42% of HIV seropositive women were depressed, based on reporting a CES-D score of >16 for 75% of more of study visits. Assuming that the population proportion of participants with elevated depressive symptoms in the placebo arm at the end of the study is 0.42, then with 30 participants per arm, we will have 80% power to detect that the corresponding treatment proportion is <0.12 or >0.76. For health related quality of life, Mrus et al. reported a mean for the overall health domain of HRQoL in women engaged in HIV treatment of 71.4, with a standard deviation of 13.8. Using this standard deviation, with 30 participants per arm, we will have 80% power to detect if the absolute mean between-group difference in this quality of life measure at the end of the study is 10.2 points or greater, based on a two-sample t-test at the 0.05 two-tailed significance level. In summary, we are confident that we can achieve a medium to large effect size across multiple outcomes with the proposed N.

**Analyses:** With respect to quantitative data, we will compare each outcome between groups using mixed- model regression analyses, with subject as a random effect. Fixed covariates will include time in study (baseline, end of treatment, 3 month follow-up) and time since diagnosis. Other covariates, such as education, socioeconomic status, and history of exposure to traumatic events will also be considered. We will consider exploratory mediational and moderational analyses, based on procedures outlined by Hayes. We will assess adherence in the active treatment arm, in particular to determine if adherence is related to change in the primary outcome. We will perform exploratory multivariate analyses among the outcomes, including graphical methods and the calculation and testing of correlations and partial correlations. We will examine patterns in missing data in order to see if missingness is related to measured patient characteristics. We will adjust for missing data using multiple imputation as appropriate. We will adjust for multiple comparisons using the method of Hothorn, Bretz and Westfall. Statistical analyses will be performed using “R” software.

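### Does returning the Zoom practice notes only once, at program end, undermine the weekly adherence data and the analysis built on them?

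*Combined protocol and SAP*

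**What the plan says.** Four parts of the protocol and one of the SAP bear on this.

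- **Protocol, Secondary Outcomes: HIV/Physical Health, antiretroviral adherence paragraph:** "Data on self-reported adherence will be collected each week using the participant" weekly skills form.
- **Same section, Weekly adherence to skills:** the diaries feed a practice rating: "These diaries will be used to generate a rating of adherence to out of session practice guidelines". Under Zoom the notes are posted to intervention-arm women, who fill them in over the 10 weeks. Then: "Participants will then be asked to mail back the completed practice notes (via a pre-paid envelope) at the end of the program".
- **Protocol, Data monitoring:** "The study staff will review all data collection forms on an ongoing basis for data completeness and accuracy as well as protocol compliance". Also: "Data verification will be performed weekly by a study research assistant".
- **Protocol, Retention paragraph:** "We will make concerted efforts to maintain contact with individuals who discontinue the intervention but are still willing to complete follow-up assessments". The Feasibility paragraph after it tracks "the number of treatment and assessment sessions completed by all enrolled participants".
- **SAP, Analyses (repeated in the protocol's Data analytic plan):** "We will assess adherence in the active treatment arm, in particular to determine if adherence is related to change in the primary outcome". Missing data are handled by examining whether missingness relates to measured characteristics, and by multiple imputation where suitable.

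**The concern.** Read together, these statements seem not to fit. If forms arrive once, after the last session, staff cannot review them while the program runs, and gaps appear only when it is too late to fill them. A single bundle also cannot show whether a daily diary was kept daily or written up afterwards.

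The worry then reaches the analysis. The practice rating is a natural exposure for the active-arm question of whether women who adhere more gain more resilience. A woman who stops attending may complete her outcome assessments and never post the envelope. If those women are the least adherent, the analysis keeps only the better adherers. A weak association could then reflect how paper came back and not how the intervention works. The missing-data text says nothing specific about unreturned notes.

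**Working it through.** The plan gives no figure for this analysis, so there is none to reproduce. The check has three steps.

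**1. The wording, side by side**

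| Statement | Strict reading | Reading that fits the Zoom rule |
|---|---|---|
| Adherence collected each week | Staff receive a form each week | The woman records each week and returns the notes later |
| Forms reviewed on an ongoing basis, data verified weekly | Every form checked during the program | Forms checked as they are received |

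The Zoom rule is the specific one, and the notes are still completed during the program. The passages are in tension but do not contradict each other. Table 4 (the assessment timeline) is not in the text available for this review and may state a return schedule.

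**2. What is still known about a woman who stops early but attends assessments**

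- Antiretroviral adherence: it is in the baseline battery, and the same self-report measures are repeated post-treatment and at 3 months in both arms (Study procedures and data collection). The between-arm comparison does not depend on the mailed notes.
- Sessions completed: tracked for everyone enrolled.
- Weekly progress notes, and an exit interview that asks about use of the skills (same section).

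What can be lost is the form-based weekly and practice data, in the intervention arm, under Zoom.

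**3. Size of the loss in the active-arm analysis**

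Inputs from the documents: 30 women per arm (SAP, Power) and a 10-week program. Assumptions: a true adherence–change correlation of 0.50, bivariate normal data, a two-sided 0.05 test, and k = 3, 7 or 9 women with outcomes but no notes.

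*Forms.* 30 × 10 = 300 in total; 30, 70 or 90 belong to those k women. These are upper bounds. Weeks after a woman stops would be blank under any return schedule, so only notes written but not posted are at stake.

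*The benchmark.* In Phase I, 3 of 13 enrollees (23%) did not take part, and 0.23 × 30 ≈ 7. But the same section goes on to describe three women as lost to follow-up. Women who never started have no practice to record, and women lost to follow-up give no later outcome. The rate does not describe women with outcomes and no notes, so all three values of k are bare assumptions.

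*Worst case: the k lowest adherers are missing.* With f = k/30, a = Φ⁻¹(f) and λ = φ(a)/(1 − f), the variance of adherence among the women left is v = 1 + aλ − λ². The expected correlation is 0.5√v / √(0.25v + 0.75). The slope's standard error grows by roughly √(30 / ((30 − k)v)).

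| k | v | r, formula | r, simulated | Slope, simulated | SE ratio | Power, lowest k missing | Power, random k missing |
|---|---|---|---|---|---|---|---|
| 0 | 1 | 0.50 | 0.49 | 0.50 | 1 | 83% | 83% |
| 3 | 0.712 | 0.438 | 0.44 | 0.50 | 1.25 | 66% | 79% |
| 7 | 0.550 | 0.394 | 0.39 | 0.50 | 1.54 | 49% | 71% |
| 9 | 0.493 | 0.376 | 0.37 | 0.50 | 1.70 | 41% | 66% |

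Example for k = 9: √(30 / (21 × 0.493)) = √2.90 = 1.70. Simulations used 40,000 data sets per row; a rerun agreed on power to within about one point.

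The correlation falls because the spread of adherence is cut. The slope does not move, because selection on the exposure alone leaves the regression of outcome on exposure intact.

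*If loss is unrelated to adherence,* the smallest correlation detectable with 80% power is tanh((1.96 + 0.84)/√(m − 3)) for m women: 0.49 at m = 30, and 0.52, 0.56 and 0.58 at m = 27, 23 and 21.

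**The case for a change.** The best case for a change is that it would be cheap and would suit a pilot whose purpose is to test procedures. Reading the monitoring text as review on receipt still leaves no completeness check while a gap can be mended. If women without notes are those who practised least, missingness depends on the missing value itself, and the SAP names neither an auxiliary variable nor a sensitivity analysis for that. Zoom assessments are already completed in REDCap or verbally, so weekly capture would need no new system.

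Part of this stands. There is no in-program check of these notes under Zoom, no stated way to recover them from a woman who stops, and no means of dating the entries. The drop in power is real under the worst-case assumptions, and it applies to the regression test as much as to the correlation.

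The rest is weaker. The SAP does plan to examine whether missingness relates to measured characteristics, and sessions completed is an obvious one to look at. Weekly electronic capture is not clearly better. It means up to 10 prompts per woman in one arm only, and prompting may itself raise practice, the behavior being measured. It would recover nothing from women who never start and nothing for the weeks after a woman stops.

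**Conclusion.** No change to the plan is needed. The single return under Zoom is a loose fit with the weekly-collection and monitoring statements, but each can be read consistently with it. The data at risk are notes written and never posted, in one arm, under one mode of delivery, for one exploratory analysis in a feasibility pilot. The SAP does not even fix which measure of adherence that analysis uses.

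The possible cost is precision: power of 41% to 66% against 83% in an assumed worst case, 66% to 79% if loss is unrelated to adherence, and no loss if every envelope comes back. These figures rest on an assumed correlation of 0.50 and on assumed counts of missing women. The unchanged slope rests on a linear relation and on missingness that depends on adherence alone; if it also depended on outcome, some bias could arise.

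What remains is detail that analysts would ordinarily supply: counting the women who returned notes, saying how the others were treated, and using session counts alongside the practice rating.

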### **Participant remuneration.**

Participants will receive up to \$293 over the course of the study, including \$25 for their time after each of the assessment visits (i.e., baseline, post-treatment, 3-month follow-up, and optional qualitative exit interview), \$25 for interview questions related to COVID-19, as well as \$12 reimbursement for attending all study visits (either in person or via Zoom).

Participants may be remunerated via eCheck or Forte cards. If study visits are conducted virtually, Forte cards will be mailed to participants' homes for the purposes of remuneration during the study.

### **Foreseeable risks and discomforts.**

It is unlikely that participants will be at any risk for physical harm resulting from study participation. Participants may find some of the questions covered in the assessments to be emotionally upsetting. Participating in a counselling study (for resilience) can be difficult, because it may involve discussing personal matters. As with any study, there is always the risk of inadvertent breach of confidentiality. This is of particular importance here because participants are living with HIV, which may be stigmatizing. An additional discussion of how we minimize these risks is described below.

### **Minimization of risks.**

It is unlikely that participants will be at any risk for physical harm resulting from study participation. In the event that any study procedures result in significant distress, the participant will be given the opportunity to cease study participation. All research study staff will be thoroughly trained in assessment procedures. If a participant is determined to be in distress or actively suicidal and at risk for self-harm during any study procedure, study staff will contact the PI ([name]) or another trained clinician, so that appropriate clinical intervention is executed. Any participant who scores greater than or equal to a 23 on the CES-D will be evaluated (either in person or via Zoom) by a licensed psychologist or another qualified provider/clinician and referred for additional services as needed. The group facilitators will participate in regular supervision. We have added a DSMB that will convene at least annually to afford additional, external review of study procedures, participant safety, and adverse events.

Additionally, [name] has been involved with numerous local and national studies of persons with HIV and has considerable experience implementing measures to protect confidentiality. Some of these steps include in-service trainings on confidentiality and the assignment of study ID numbers. Staff at all sites who conduct participant recruitment, screening, enrollment, and assessments will have been trained in ethical human subjects research, screening and interviewing techniques, to minimize participant risk as much as possible; this includes all staff at non-Partners sites. All data will be kept confidential, under lock-and-key, accessible only to trained study staff. Participants' data will be identified by an ID number only, and a link between names and ID numbers will be kept separately under lock and key. Any paper-based assessments will be stored under lock and key within a secure office space accessible only to approved study staff. The study database will be secured with password protection and accessible only to approved study staff. Participants will be asked to sign a confidentiality statement prior to the inception of group sessions (if the baseline assessment is conducted in person) or verbally consent to such an agreement (if the baseline assessment is conducted via Zoom).

### **Expected benefits.**

It is possible that there will be no direct benefit to participants in the current study. However, participants may benefit from participation via an increased understanding of how to optimize well-being among older women living with HIV, and that may improve the care of this population in the future. Participants may also feel a sense of purpose that they are contributing to work that may help others. Participants are also provided financial remuneration for their participation.

### **Equitable selection of participants.**

Participants will be biologically born women, living with HIV, age 50 years or older, and English speaking. Participants must be able to provide informed consent and agree to study procedures (e.g. completion of assessments and intervention program). The patient population will be comprised of individuals of varied racial/ethnic and socioeconomic backgrounds. All participants meeting inclusion criteria will be offered the opportunity to participate. We will not exclude participants based on minority status.

### **Data analytic plan.**

Quantitative data will be entered in an on-going fashion (into REDCap data management system), and will be analyzed using SPSS, "R", and QSR NVivo qualitative software, version 9, after being thoroughly checked and cleaned as appropriate. [name] has the full support of a biostatistician ([name]) for all statistical analyses. We will compile descriptive statistics to examine intervention acceptability and feasibility as described above, as well as to examine indicators of change on measures of various psychosocial outcomes. We will compare each outcome between groups using mixed model regression analyses, with subject as a random effect. Fixed covariates will include time in study (baseline, end of treatment, 3-month follow-up) and time since diagnosis. Other covariates, such as education, socioeconomic status, and history of exposure to traumatic events will also be considered. We will consider exploratory mediational and moderational analyses, based on procedures outlined by Hayes. We will assess adherence in the active treatment arm, in particular to determine if adherence is related to change in the primary outcome. We will perform exploratory multivariate analyses among the outcomes, including graphical methods and the calculation and testing of correlations and partial correlations. We will examine patterns in missing data in order to see if missingness is related to measured patient characteristics. We will adjust for missing data using multiple

imputation as appropriate. We will adjust for multiple comparisons using the method of Hothorn, Bretz and Westfall. Statistical analyses will be performed using “R” software.

All qualitative data resulting from exit interviews will be analyzed using standard qualitative methodologies described by the Office of Behavioral and Social Sciences Research at the National Institutes of Health. Specifically, data will be analyzed using content analysis, an iterative, multi-step process as described by Miles and Huberman and Strauss and Corbin. The investigators will use NVivo software (version 10) to organize data and to facilitate analyses. Two study team members will independently review the transcripts in order to generate an overarching thematic framework for data interpretation, in which major and minor themes are identified. Using multiple coders also enhances the validity of the analysis. The investigators will compare their thematic frameworks for consistency, and any discrepancies will be discussed until there is agreement on the thematic framework. Data will be reexamined, messages will be extracted and highlighted, and ongoing discussion between coders will allow for further theorizing and making interconnections between research questions, coding categories, and raw data.

